1 BACKGROUND/SCIENTIFIC RATIONALE

Irritable bowel syndrome (IBS) is a common but incompletely understood condition that leads to significant morbidity and substantial health care expenditures (1,2). IBS is likely a multifactorial disorder including disordered motility, immune activation, gut barrier dysfunction, visceral hypersensitivity, and altered brain-gut interactions (3–5).

The role of the gut microbiota is increasingly being recognized for its potential role *in the pathogenesis of IBS*. Humans are host to a diverse community of microbes collectively known as the human microbiota, of which the vast majority live in the gut (6). The gut microbiota normally interacts closely with the intestinal epithelial cells as well as the enteric immune and nervous system, which comprises the microbiota-gut-brain axis (7). There is a symbiotic relationship between the microbiota and host with the gut microbiome providing essential functions, including maintenance of the gut epithelial barrier and immune function (8). However, alterations in the structure and community function of the fecal microbiota may have a significant role in the pathogenesis of human disease, including IBS. Acute gastroenteritis leads to an increased risk for development of post-infectious IBS and is associated with altered gut microbiota, increased permeability and immune activation (9–11). Further evidence of the role of gut microbiota in IBS is shown by experiments where transfer of microbiota from patients with IBS to germ-free mice leads to rapid GI transit, impaired gut barrier function, and visceral hypersensitivity (12,13).

Several studies have reported an increase in the relative abundance of Firmicutes, a reduction in the relative abundance of Bacteroidetes, and decrease in microbial diversity (14–16). However, studies are often conflicting and a specific microbial signature has not been discovered to date in IBS (17–19). Incomplete phenotypic characterization, small sample sizes, the cross-sectional nature of study design, and probable heterogeneity of the patient populations also limited prior studies. In addition, previous studies have not taken differences in diet or stool consistency into consideration despite the fact that these factors heavily influence the composition of the gut microbiota (20,21).

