4 ELIGIBILITY CRITERIA

IBS Patients:

200 consecutive adult subjects \geq 18 years of age at screening who meet the following inclusion and exclusion criteria will be eligible for enrollment:

Inclusion criteria:

- Rome IV criteria for IBS-D
- Subjects will be asked to avoid Pepto-Bismol for 2 weeks prior to GHBT.
- Subjects will be instructed to avoid eating or drinking for 8 hours and avoid smoking for 6 hours prior to the test
- Have colonoscopy or sigmoidoscopy with mucosal biopsy within the past 2 years prior to enrollment
- Have an average score of 4 or higher over a 7-day pre-screen taking online symptom surveys assessing abdominal pain and bloating

Exclusion criteria:

- Underlying celiac disease
- Inflammatory bowel disease
- Other organic disease that could explain their symptoms.
- History of GI tract surgery, except for appendectomy
- Narcotics, antibiotics taken within 3 months or probiotics taken within one month prior to enrollment will not be permitted.
- Previously received formal dietary education, including a low FODMAP diet, for treatment of IBS.
- Previously received antibiotics, such as rifaximin, for treatment of IBS or SIBO.
- Women who are pregnant
- Women who are breastfeeding

Additional IBS subjects and Healthy Controls:

50 consecutive adult subjects \geq 18 years (25 IBS-D and 25 healthy controls) who are undergoing colonoscopy for clinical purposes (e.g. colon cancer screening)

For IBS subjects:

Inclusion criteria:

- Rome IV criteria for IBS-D

Exclusion criteria:

- Underlying celiac disease
- Inflammatory bowel disease
- Other organic disease that could explain their symptoms.
- History of GI tract surgery, except for appendectomy
- Narcotics, antibiotics taken within 3 months or probiotics taken within one month prior to enrollment will not be permitted.
- Women who are pregnant
- Women who are breastfeeding

For healthy controls:

Exclusion Criteria:

- History of chronic GI disorder, such as irritable bowel syndrome, inflammatory bowel disease, and small intestinal bacterial overgrowth
- Narcotics, antibiotics taken within 3 months or probiotics taken within one month prior to enrollment will not be permitted
- Women who are pregnant
- Women who are breastfeeding

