5 SUBJECT ENROLLMENT

Most patients with irritable bowel syndrome are seen in gastroenterology or general medicine clinics. IBS-D patients will be recruited from gastroenterology and general medicine clinics at Taubman Center and in the satellite clinics within the University of Michigan Health System. We will also be sending out letters to patients identified from DataDirect as eligible for the study. Eligible IBS-D subjects will be contacted and given material explaining the nature of the study and introduction to a low FODMAP diet. They will be given time to read the materials. If they choose to participate, they will undergo a one week pre-screening an 11-point numerical rating scale (NRS) for abdominal pain and bloating for 7 days. If the subjects qualify through the pre-screen, they will sign the consent document in the presence of the PI and/or Designee. IBS-D subjects will be enrolled on a first come, first served basis. This approach will ensure that IBS-D subjects are representative of the population of patients with IBS in Southeast Michigan.

Emails to providers in the General Medicine and Gastroenterology clinics in the University of Michigan System, public advertisements, telephone calls, and web postings on UMClinicalStudies.org will also be utilized to recruit IBS-D subjects.

IBS subjects who do not meet inclusion/exclusion criteria will not be enrolled in the study. All data collected from IBS-D subjects who are screen failures will be saved for data analysis.

IBS subjects and healthy controls who are undergoing colonoscopy will be approached in the Medical Procedures Unit to determine their interest in participating in the optional sub-study and to determine their eligibility.

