Mucosal Samples: If subjects consent to participate in this optional sub-study, mucosal biopsies will be taken from eligible subjects who are scheduled to undergo a colonoscopy for clinical purposes (e.g. to rule out alternative causes of symptoms or screening for colon cancer). In addition to the IBS subjects recruited to participate in the clinical trial, we will recruit an additional 25 IBS subjects as well as 25 healthy controls undergoing colonoscopy for clinical purposes (e.g. colon cancer screening) to determine how host-microbial interactions may impact on IBS vs. healthy controls.

Mucosal biopsies will be utilized to generate human intestinal enteroids to study host-microbial interactions determining response to treatment in IBS. Four mucosal biopsies will be obtained from normal appearing mucosa in the ileum, ascending and sigmoid colon (total of 12 mucosal biopsies per patient), placed in a sterile cryovial on ice, and immediately stored at -80°C for long-term storage.

Sequencing and Data Analysis:

(i) MiSeq Illumina Sequencing: DNA samples will be submitted to the University of Michigan Host Microbiome Initiative under the Microbiome Explorers Program and will be processed using the MiSeq Illumina sequencing platform. 16S rRNA gene libraries will be constructed using primers specific to the V4 region.

(ii) OTUs and Diversity Measurements: The open-source software program, Mothur, will be used following the steps outlined in the Mothur MiSeq SOP (66,67). The 16S rRNA gene sequencing profiles will be assessed using metrics for α diversity (such as Shannon or inverse-

Simpson indices) and β diversity-based distance measures between samples, such as θ_{yc} or Bray-Curtis (68,69). Community types will be identified using unsupervised clustering algorithms, and individual operational taxonomic units (OTUs) will be identified and compared between/within patients (see Biostatistical analysis).

(iii) Quantitative PCR Targeting the 16S rRNA Gene: qPCR will be used to quantify the total number of 16S rRNA gene copies/gram. Reactions will be performed on a CFX Connect Real-Time PCR detection system (Bio-Rad Laboratories; Hercules, CA) with universal 16S rRNA gene primers as previously described (33).

Specific Aim 3: Develop a predictive model to identify subsets of IBS-D patients responsive to treatment.

3A. Approach:

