We will develop and validate a predictive model of response to low FODMAP diet using data from the subjects randomized to a low FODMAP diet (Aim 1) combined with existing data from a separate cohort of IBS-D subjects previously treated with a low FODMAP diet (HUM 00053274).

3B. Experimental Methods:

We will use the combined cohort of patients treated with a low FODMAP diet (Aim 1 and HUM #00053274), which will be split into a training set from a random sample of 80% of the data while the remaining 20% of the data will serve as the test set. Using a random forest model, 5x2 nested cross-validation (CV) will be performed within the training set for model selection and hyperparameter tuning. The candidate models will be compared by testing for overlap of confidence intervals for area under the curves (AUCs, two-sided test). Once a final model is selected, model performance will be evaluated on the test set.

Study Timeline:

Figure 1 IBS Subject Timeline

Schedule of Events - Low FODMAP Group

Visit Number	Pre-Visit	Visit 1	Visit 2	Visit 3	Visit 4	Visit 5
Visit Description	Pre-screening (Phone/in person)	Baseline (Phone/in person)	Monitoring (Phone/in person)	Monitoring (Phone/in person)	Monitoring (Phone/in person)	Monitoring/Outcomes (Phone/in person)
Time point	Eligibility	Day 0	Day 7±3 days	Day 14±3 days	Day 28±3 days	Day 35±3 days
7 day pre-screening questionnaire	X					
Informed Consent	X					
Medical History /Physical Examination		X	X	X	X	X
Urine pregnancy test (Females of childbearing age)		X				
Washout	X					
Questionnaires		X		X		X

3-day food diary		X				
24-hour dietary recall			X	X	X	X
GI nutrition consultation		X		X		
Colonoscopy with mucosal biopsies (optional)	X					
Serum Cytokine Profiles (optional)		X				X
Buccal swab collection (optional)		X				
Glucose hydrogen breath testing		X				X
Stool collection for fecal microbial analysis		X (3 baseline samples)		X	X	X
Randomization	X					
Dietary Compliance			X	X	X	X
Adverse Events Monitoring			X	X	X	X

*Female participants capable of bearing children will be required to attend visit 1 in person for the pregnancy test

*During COVID-19 pandemic, all hydrogen breath tests will be conducted remotely

Schedule of Events – Rifaximin Group

*Female participants capable of bearing children will be required to attend visit 1 in person for the pregnancy test

*During COVID-19 pandemic, all hydrogen breath tests will be conducted remotely

Visit Number	Pre-Visit	Visit 1	Visit 2	Visit 3	Visit 4	Visit 5

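### No minimum interval separates bowel preparation for endoscopy from the baseline stools and breath test, so recovery after a recent preparation could be counted as a change in diversity under treatment

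*Combined protocol and SAP*

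**What the plan says.** Section 4 (Eligibility Criteria) requires trial patients to "Have colonoscopy or sigmoidoscopy with mucosal biopsy within the past 2 years prior to enrollment". This is an upper limit only.

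Section 6, Aim 2, Mucosal Samples, adds an optional sub-study in which "mucosal biopsies will be taken from eligible subjects who are scheduled to undergo a colonoscopy for clinical purposes". Randomised patients can take part, because the 25 extra IBS patients and 25 controls come "In addition to the IBS subjects recruited to participate in the clinical trial". Both Schedules of Events mark this procedure, "Colonoscopy with mucosal biopsies (optional"), in the Pre-Visit column. Three baseline stools and the row "Glucose hydrogen breath testing" are marked at Visit 1, Day 0.

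Sections 3 and 4 protect the baseline with rules on antibiotics (3 months), probiotics (1 month) and bismuth (2 weeks before the breath test), and on fasting, smoking and a low-carbohydrate diet before the breath test. The schedules have a Washout row at the Pre-Visit, but it is not defined there. Bowel preparation appears nowhere.

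Section 1 holds that diet and stool consistency strongly affect the microbiota, and criticises earlier work because "previous studies have not taken differences in diet or stool consistency into consideration".

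Section 2 makes change in fecal diversity from baseline the primary aim of Aim 2, with a hypothesised 10-15% rise on the low FODMAP diet. Section 10 tests it with a paired t-test and averages the three pre-treatment samples for the baseline.

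**The concern.** A patient whose work-up colonoscopy took place shortly before Day 0 meets every written criterion. Suppose bowel cleansing temporarily disturbs the stool community. All three baseline samples would then carry the disturbance, and the samples at weeks 2, 4 and 5 would show recovery from it. If the disturbance is a fall in diversity, recovery has the same sign as the Aim 2 hypothesis.

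The planned analysis has no means of separating the two. Section 10 relies on pairing to remove bias, but pairing removes only stable differences between patients. Averaging three samples does not help if all three follow the preparation. There is no untreated arm. Baseline SIBO status, and its persistence at week 5, rest on the same unprotected baseline.

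The omission is at odds with the plan's own approach, which takes care to keep other recent exposures away from these measurements.

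**Working it through.** **Timing.** The Pre-Visit column has no day number; its time point is Eligibility. Section 5 says: "If the subjects qualify through the pre-screen, they will sign the consent document". A research biopsy needs consent, so on that order a sub-study colonoscopy falls between consent and Day 0. A qualifying endoscopy may fall at any time in the previous 2 years. In neither case is a minimum gap given.

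**The plan's own figures.** None bears on this point. No SD for change in diversity is given, so the power statement for Aim 2 cannot be reproduced.

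**Inputs from the documents.** Hypothesised rise 10-15% (section 2); within-arm paired t-test (section 10); 32 per arm in section 10, or about 100 per arm from the 200 patients in sections 2, 4 and 6; endoscopy window 2 years, taken as 104 weeks.

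**Inputs that are assumptions.**
- f: share of an arm with a recent preparation.
- x: percentage by which the measured baseline change is distorted (the depression at baseline), taken as 10% or 20%.
- s: SD of the percentage change in diversity, taken as 10-20%.
- Full recovery by the end of the intervention, and a two-sided 5% test.

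**Formula.** Spurious mean rise = f × x, in percentage points.

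**Low case.** If endoscopies are spread evenly over the window, the share within 4 weeks of baseline is f = 4/104 = 3.8%. The rise is 0.038 × 10 = 0.4 to 0.038 × 20 = 0.8 points.

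**Clustered cases.** For f = 10%: 0.10 × 10 = 1.0 and 0.10 × 20 = 2.0 points. For f = 25%: 0.25 × 10 = 2.5 and 0.25 × 20 = 5.0 points.

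**False-positive rate.** The paired t-test was simulated with no treatment effect. Ranges run over s = 10-20%.

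| f | x | Spurious rise (points) | n = 32 | n = 100 |
|---|---|---|---|---|
| 3.8% | 10% | 0.4 | 0.05 | 0.05-0.07 |
| 3.8% | 20% | 0.8 | 0.05-0.06 | 0.07-0.11 |
| 10% | 10% | 1.0 | 0.06-0.08 | 0.07-0.16 |
| 10% | 20% | 2.0 | 0.08-0.14 | 0.16-0.39 |
| 25% | 10% | 2.5 | 0.10-0.24 | 0.23-0.62 |
| 25% | 20% | 5.0 | 0.24-0.54 | 0.62-0.97 |

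To reach even the lower end of the hypothesised 10-15%, half of an arm would have to be affected with a 20% depression (0.50 × 20 = 10 points). With f = 0 the spurious rise is zero and the error rate is the nominal 5%.

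**The case against.** The strongest reply is that the mechanism and its size are not in the documents. Section 1 names diet and stool consistency, not bowel preparation. Nothing states that cleansing lowers diversity, by how much or for how long. That stands, and it is why the table is a range and not an estimate.

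The share affected may also be small. Section 5 recruits through general medicine clinics, database letters and advertisements as well as gastroenterology clinics, and the sub-study is optional and of unstated size. That stands too. But section 6 gives ruling out other causes of symptoms as one reason for the colonoscopy, so clustering of recent work-ups cannot be excluded.

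The reach is limited. A between-arm comparison would be protected in expectation by randomisation, and section 10 calls the Aim 2 work exploratory. The planned primary test is nevertheless within arm. Checking the 2-year criterion needs the endoscopy date, so part of the remedy may already be in the source records.

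A reader might infer more than the documents support:
- *That the trial times a colonoscopy right before baseline.* The column has no day and also holds a washout, and the washouts in the text run from 2 weeks to 3 months. The colonoscopy is a clinical one.
- *That the baseline breath test turns falsely negative.* No direction is given.
- *That the sub-study colonoscopy disturbs the symptom pre-screen.* Consent follows that week, so the procedure would come after it.
- *That patients with mucosal samples are affected most.* Their biopsies are for enteroids, and nothing shows that an artefact in baseline stool carries over to them.
- *That 7-60% of the hypothesised effect is the expected size.* That range follows from a 10-30% share and a 10-20% depression (0.1 × 10 / 15 to 0.3 × 20 / 10), neither of which has a source.

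**Conclusion.** The gap is real: no minimum interval, an undefined Washout row, and a within-arm comparison with a baseline that may follow bowel preparation. The resulting bias is possible, but its size is unknown. Under the stated assumptions it runs from under 1 point, with little effect on the error rate at 32 per arm, to several points and a clearly inflated error rate if recent work-ups cluster. That cleansing disturbs diversity, in which direction and for how long, is itself an assumption. Without the date of the last preparation, nobody could show that the effect is negligible. This is a worthwhile, low-cost improvement. It does not by itself invalidate Aim 2, and it is no argument against a between-arm contrast.

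**What to change.** 1. Define the Washout row in both schedules, with a matching line in section 4, to include a minimum interval between any bowel preparation and the baseline stools and breath test. The sponsor should justify the length. Four weeks, in line with the one-month probiotic rule, is one option, but nothing in the documents shows that it is the right one for bowel preparation.
2. Record the date of the last bowel preparation for every patient.
3. Pre-specify a sensitivity analysis of diversity change, and of the analyses that use baseline SIBO status, excluding patients inside the interval. For patients already enrolled, this needs only the endoscopy dates.

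The cost is one protocol line, one date field and one extra analysis, with no added procedure. Some patients, mainly in the biopsy sub-study, would start a few weeks later.

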8 DATA ANALYSIS

Procedure for Accounting for Missing, Unused, and Spurious Data: The primary outcome measure in our study is changes in mean daily pain or bloating after intervention with rifaximin or low FODMAP diet compared with baseline. We will use multiple imputation with 10 imputed datasets to replace missing values on outcome and predictor variables [77]. If 10 imputed datasets are not sufficient to ensure stability of estimates, we will use 20 imputed datasets. This allows for maximal use of available data while maximizing statistical power.

9 QUALITY CONTROL AND QUALITY ASSURANCE

The PI and Study Coordinator will be responsible for Quality Control and Quality Assurance and will be performed in accordance with Standard Operating Procedures at the University of Michigan.

10 STATISTICAL CONSIDERATIONS

Aim 1:

All of the interventional analyses will be analyzed on an intention-to-treat basis. Each IBS-D subject will act as his/her own control for analysis of the effects of either rifaximin or low FODMAP diet intervention. This paired design inherently eliminates a significant amount of bias/confounding and affords increased statistical power. We will power our study to detect a $\geq 30\%$ improvement in mean daily bloating or abdominal pain after intervention compared with baseline. Using available data from a US study on low FODMAP diet in IBS patients (42), we conservatively estimate that we will require 14 IBS-D subjects in each arm to have $>90\%$ power to detect a mean difference of 1.7 in abdominal bloating scores after intervention via paired t-tests with the expected standard deviation (SD) of ± 1.8 . Thus, our expected enrollment of 32 IBS-D subjects in each arm will be more than sufficient for analyzing this aim (see biostatistical analysis for Aim 2), even if the SD is nearly two-fold larger than expected.

Aim 2:

We will examine both inter- and intra-individual variability in microbiota-derived metrics. We plan to use a paired design to eliminate a significant amount of bias/confounding and increase statistical power. We anticipate that there will be some variability in the three samples collected prior to treatment, and various techniques will be employed to average these data so they are incorporated as the baseline. For example, for α diversity (Shannon index) a simple average of the three time points will be sufficient to

establish a baseline α diversity. Similar techniques will be applied to other community structure metrics, to create “deltas” between post-treatment time points and the baseline.

These microbe-derived metrics and accompanying clinical variables will be initially analyzed through descriptive statistics before/after intervention. Histograms and measures of frequency or central tendency/spread will be used to optimize variable constructions. Subsequently, initial bivariable longitudinal analyses in an inter-individual fashion (assessing group-wide trends before/after intervention) that also account for the paired nature of the data (intra-individual) will be employed for categorical data (McNemar’s test) and continuous data (paired t-test), or their non-parametric equivalents for data not normally distributed. Multiple comparisons will be made for individual OTU abundance metrics, with a focus on the most abundant taxa. However, we will avoid a high false discovery rate through use of linear discriminant analysis effect size (LEfSe) analysis (70). Similar to Aim 1, we will power our study using a paired t-test based on the primary outcome to detect a change in diversity at the end of the intervention compared with baseline. In addition, we will also examine intermediate endpoints or longitudinal trends over time to determine if these are important. If this is the case, we will also use mixed model analyses with repeated measures.

Although this work is exploratory, we wanted to ensure that we will have sufficient power to detect notable differences in microbial and functional characteristics with our planned recruitment base. Based on prior studies with low FODMAP diet in IBS patients (42,45,71), we conservatively estimate that 60% of IBS-D subjects will respond to treatment. We further expect that only those IBS-D subjects who respond to a low FODMAP diet will show changes in fecal microbial diversity. Given our sample size of 32 subjects per arm, we will have >90% power to detect a mean difference ≥ 0.4 in θ_{YC} (a measure of β -diversity) between responders and non-responders. As we are already seeing differences in θ_{YC} of this magnitude or greater, this suggests we are appropriately powered to detect meaningful differences in the microbiota between groups even if our standard deviation is 2-fold greater than expected.

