Despite our advances in understanding the pathophysiology of IBS, there are still **unmet needs** in terms of treatment options. Rifaximin is a non-absorbable antibiotic that has been shown to improve symptoms in the diarrhea-predominant subtype of IBS (IBS-D) (31,32). However, mechanisms by which rifaximin leads to improvement in IBS-D are still unknown. In vitro studies suggest that rifaximin may prevent changes in barrier dysfunction and reverse mucosal inflammation by modulating bacteria in the small intestine (33). Conversely, prior studies have not demonstrated significant effects of rifaximin on fecal microbial composition (34,35). This is likely because rifaximin is insoluble in the colon and has antimicrobial effects primarily in the small bowel (36). Furthermore, rifaximin leads to improvement in symptoms in *only 40% of IBS patients* with a therapeutic gain of 9% over placebo. Because of these observations, one could argue that rifaximin may be effective only in those IBS patients who have concomitant SIBO. Indeed, a recent study demonstrated that those IBS patients with SIBO had a significantly increased response to rifaximin compared with those IBS patients without SIBO (37).

Dietary modification has also been advocated as a potential treatment option in IBS-D. The vast majority of IBS patients believe certain foods trigger their IBS symptoms (38). Fermentable oligosaccharides, disaccharides, monosaccharides, and polyols (FODMAP) are short-chain, poorly absorbable carbohydrates. Recently, a diet low in FODMAP has been shown to improve symptoms in up to 76% of IBS patients (39,40). However, two recent randomized controlled trials failed to show a low FODMAP diet was superior to traditional IBS dietary advice in controlling symptoms (41,42). Furthermore, improvement in symptoms was reported by *only 50% of patients on low FODMAP diets*. Moreover, the exact mechanism by which a low FODMAP diet improves symptoms in IBS is still unknown. It is postulated that the gut microbiota are critical in generation of symptoms in the presence of dietary FODMAPs and lead to production of gases, including hydrogen, CO₂, and methane. This may generate symptoms in IBS particularly in the setting of visceral hypersensitivity (43).

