Trial Protocol: In order to minimize unequal allocation between arms, IBS-D subjects will be randomized using block randomization with random permuted sizes of 2 or 4 in a 1:1 ratio into two arms: one group will undergo treatment with rifaximin 550 mg three times daily for 14 days. The second group will be placed on a low FODMAP diet (≤ 9 grams per day as previously described) for 4 weeks (40,64,65). IBS-D subjects undergoing dietary intervention will undergo consultation with a bionutritionist knowledgeable in low FODMAP diets. A diet plan will be implemented and individualized to subjects based on information from their dietary history. Written information regarding allowable vs. non-allowable food items will be provided to IBS-D subjects and bionutritionists will be available during the study for further education. IBS-D subjects randomized to the low FODMAP diet group will meet with the GI nutritionist at the completion of the 2nd week of dietary intervention to answer any potential questions regarding the diet. IBS-D subjects will complete a 24-hour dietary recall each week or every two weeks during the 4-week dietary intervention to ensure compliance.

Symptom Assessment: IBS-D subjects will record stool frequency, BSFS, and symptom scores for abdominal pain and bloating daily on a diary card. IBS-D subjects will complete questionnaires on a weekly basis during study visits to determine changes in symptoms. Responders to intervention arm (both rifaximin and low FODMAP diet) will be defined as $\geq 30\%$ reductions in mean daily pain or bloating compared with baseline. Secondary outcomes, including reduction in IBS Symptom Severity Scale by ≥ 50 compared with baseline at the end of the interventional arm, will also be monitored. These are both considered to reflect clinically meaningful improvements in IBS (55,57). IBS-D subjects will be seen on a weekly or biweekly basis and diary cards will be collected. Adherence to medications or dietary intervention will also be assessed at that time.

Specific Aim 2: Determine using longitudinal analyses how SIBO status and fecal microbiota-derived metrics associate with response to treatment with rifaximin or a low FODMAP dietary intervention.

2A. Research Approach:

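### Aim 1 randomises rifaximin against a low FODMAP diet, but the plan specifies only within-arm before-after testing and no comparison between the arms

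*Combined protocol and SAP*

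**What the plan says.** Section 6 (Trial Protocol) sets up a randomised comparison: "IBS-D subjects will be randomized using block randomization with random permuted sizes of 2 or 4 in a 1:1 ratio into two arms". Sections 2 and 6 word Aim 1 as one treatment versus the other. The primary outcome is the change in mean daily pain or bloating from baseline. Section 6 (Symptom Assessment) adds a responder definition: "Responders to intervention arm (both rifaximin and low FODMAP diet) will be defined as" a fall of at least 30% in either score from the subject's own baseline.

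Section 10, Aim 1, calls for intention-to-treat analysis and then sets the contrast: "Each IBS-D subject will act as his/her own control for analysis of the effects of either rifaximin or low FODMAP diet intervention". It justifies this by saying: "This paired design inherently eliminates a significant amount of bias/confounding and affords increased statistical power". The only test it names is in the power statement, where 14 subjects per arm are said to give more than 90% power "to detect a mean difference of 1.7 in abdominal bloating scores after intervention via paired t-tests with the expected standard deviation (SD) of" 1.8. Section 8 deals only with missing data, by multiple imputation.

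**The concern.** The contrast that randomisation protects is rifaximin against diet. The contrast that section 10 describes is after against before, within each arm. Change from baseline is an acceptable outcome. Testing it against zero within an arm, however, mixes any treatment effect with placebo response, natural course and regression to the mean. Pairing removes stable differences between people and does nothing about these three, so the statement about bias and confounding claims too much.

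Two things follow. Taken as written, section 10 credits a fall within an arm to that arm's treatment, in a trial with no placebo or untreated arm. And the comparison that randomisation does support has no prespecified analysis, so its outcome, model and time window could be chosen after the data are seen.

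**Working it through.** **1. Reproduce the plan's figure.** Inputs from section 10, Aim 1: difference 1.7, SD 1.8, 14 per arm, power above 90%. Assumptions: two-sided 0.05 (the documents give neither alpha nor sidedness), and 1.8 read as the SD of the change (not stated).

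- Paired t-test: noncentrality (1.7/1.8)·√14 = 3.53, 13 df, critical value 2.160, power **90.4%**. With n = 13 it is 87.8%, so 14 is the smallest n that reaches 90%.
- Two-sample t-test, 14 per arm: noncentrality (1.7/1.8)·√(14/2) = 2.50, 26 df, critical value 2.056, power **67.2%**.

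The stated sample size therefore rests on the within-arm contrast.

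**2. Look for an arm comparison elsewhere.** The nearest texts do not supply one:

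- Section 2, Aim 1 item (e), says that other secondary outcomes will be compared. It names neither arms nor a test and does not cover the primary outcome.
- Section 10, Aim 2, names McNemar and paired t-tests, which are before-after tests.
- The mixed model in section 10, Aim 2, is conditional and has no arm term.
- The between-group contrast that is powered in section 10, Aim 2, is responders versus non-responders on a microbiota distance, not arm versus arm.

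**3. Non-specific improvement in the protocol's own background.** Section 1 gives 40% improvement on rifaximin "with a therapeutic gain of 9% over placebo". Read as percentage points, 40 − 9 = 31% improved on placebo. Read as a relative gain, 40/1.09 = about 37%. Either way, a sizeable share improved without the drug. Section 4 also requires an average score of 4 or higher over a 7-day pre-screen, which makes regression to the mean plausible. Its size is unknown, because the documents do not say whether that week serves as the baseline.

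**4. How often a purely non-specific fall would be significant.** Illustration only: the falls are assumed, and the documents give none. Power of the paired test uses noncentrality (fall/SD)·√n and n − 1 df. Both sample sizes are shown because section 10 has 32 per arm, while sections 2, 4 and 6 have 200 subjects (100 per arm at 1:1). SD 3.6 is twice the planned value, since section 10 itself contemplates an SD nearly two-fold larger; 2.5 is an intermediate value.

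| Assumed fall | SD of change | n = 32 | n = 100 |
|---|---|---|---|
| 0.5 | 1.8 | 33% | 79% |
| 0.75 | 1.8 | 63% | 98% |
| 1.0 | 1.8 | 86% | >99% |
| 0.5 | 2.5 | 19% | 51% |
| 1.0 | 2.5 | 59% | 98% |
| 0.5 | 3.6 | 12% | 28% |
| 1.0 | 3.6 | 33% | 79% |

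These falls would be real. The error would lie in attributing them to the treatment.

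**5. Precision of the missing contrast.** Difference detectable with 80% power, two-sample t-test on the change score, noncentrality (d/SD)·√(n/2), 2n − 2 df:

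| SD of change | 32 per arm | 100 per arm |
|---|---|---|
| 1.8 | 1.28 | 0.72 |
| 2.5 | 1.78 | 1.00 |
| 3.6 | 2.56 | 1.43 |

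For responders, take 60% (the planning rate in section 10) against 40% (the background rifaximin rate in section 1) as an example. The pooled normal formula gives z = (0.20·√n − 1.96·√(2·0.5·0.5))/√(0.6·0.4 + 0.4·0.6). At n = 32, z = −0.37, power 36%; at n = 100, z = 0.89, power 81%.

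**The case against.** The best defence is that the study is about mechanism and prediction. The hypotheses at the end of section 1 concern phenotypes and predictors of response, and neither says that one treatment is better. Section 10 also calls the work exploratory. This stands in part, and it is why a smaller remedy is offered below. But the exploratory label appears under Aim 2, whereas Aim 1 is worded as one treatment versus the other, with randomisation and a named primary outcome. Intention-to-treat says who is counted and in which arm; it does not define a contrast.

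A second objection stands in full. Comparing two treatments with no placebo arm does not reveal the specific effect of either. Only relabelling the within-arm results answers the placebo-response problem; the arm contrast answers the separate problem of an unspecified randomised comparison.

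Three stronger readings are tempting and are not supported:

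- **Reference 42.** The planning data come from a trial that section 1 cites as failing to show the diet superior to traditional dietary advice. A reader might infer that the 1.7-point change is non-specific. The comparator was another dietary treatment, so failure to beat it does not show that.
- **Turning 31% into points.** A reader might convert the placebo rate into a mean fall and so into an expected rate of significant results. That needs 1.7 points to equal a 30% fall, which no section says, and a response definition shared with the background figure. The result also depends heavily on the SD.
- **Ranking arms by p-value.** A reader might suppose that the treatments will be compared by which arm reaches significance. No section says so.

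**Conclusion.** The omission is real and matters. Aim 1 randomises 1:1 and then describes an analysis that does not use the randomisation for the primary change score or the responder outcome. The sample size confirms this, since 14 per arm is a paired-test figure (90.4% versus 67.2%, assuming two-sided 0.05 and 1.8 as the SD of change).

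The size of the resulting misattribution cannot be fixed from the documents. With SD 1.8 and assumed non-specific falls of 0.5 to 1.0 points, the paired test is significant in 33% to 86% of arms at 32 and 79% to more than 99% at 100. At twice that SD the ranges are 12% to 33% and 28% to 79%. The omission itself depends on none of these assumptions. The finding is not that the treatments lack effect, nor that within-arm falls would be spurious; it is that the planned analysis cannot say what caused them.

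**What to change.** In section 10, Aim 1:

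- Add a prespecified between-arm difference, with 95% CI, in mean daily symptom score from a linear model with arm and baseline score, by intention-to-treat with the multiple imputation already planned.
- Name one symptom and one assessment window, and state which days form the baseline. In choosing the window, note that both schedules label Visit 5 (Day 35) as the outcomes visit and that the treatments last 14 days and 4 weeks, so a common window falls at different times after treatment ends.
- Add the between-arm difference in responder proportions, with 95% CI, as supporting.
- Label within-arm changes and responder rates descriptive, not evidence of either treatment's specific effect.
- Reword the bias sentence to say that pairing removes stable between-person differences only.

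If no arm comparison is intended, the protocol should instead say that Aim 1 makes no between-arm or treatment-specific efficacy claim.

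**Cost.** No new data are needed, because pain and bloating are already recorded daily. The 32 per arm in section 10 must be reconciled with the 200 subjects in sections 2, 4 and 6, and precision restated for the arm contrast: about 1.28 points detectable at 80% power with 32 per arm and 0.72 with 100, if 1.8 is the SD of change, and more if the SD is larger. At 32 per arm the result should be read as an estimate with its interval. It gives only the relative effect of two treatments, with no masking described, so differing expectations between arms remain.
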